6. STUDY PROCEDURES

Study visits

Visits	Procedures
Visit 1 – before surgery	
- Obtain informed consent- ADL questionnaire (see next section)- Visual analog scale for pain (VAS): pain on a scale of 1 to 10 
The measurements are part of standard care and performed by caregivers
 
- Perform the following measurements: range of motion of the PIP joint of the affected finger (including noting any flexion contracture), distance fingertip to distal palmar crease (DPC), and grip strength using Jamar 2 setting.
Visit/Telephone call 2 (2-4 days after surgery)	
- Take the following questionnaire:
1. Are you able to return to activities of daily living, and what activities do you still have trouble doing? You can list the activities you are having trouble with.2. VAS3. How many oxycodone or other narcotic medications are you taking post-op4. Are you able to return to work?

	
5. Are you satisfied with the procedure, and would you choose to have it again for a similar problem?
 
- Take the ADL questionnaire (see next section)- If in person (part of standard care, only collected by study staff, measurements performed by caregivers): Perform the following measurements: range of motion of the PIP joint of the affected finger (including noting any flexion contracture), distance fingertip to distal palmar crease (DPC), and grip strength using Jamar 2 setting.
Visit/Telephone call 3 (6-8 days after surgery)	
- Take the following questionnaire:
1. Are you able to return to activities of daily living, and what activities do you still have trouble doing? You can list the activities you are having trouble with.2. VAS3. How many oxycodone or other narcotic medications are you taking post-op4. Are you able to return to work?5. Are you satisfied with the procedure, and would you choose to have it again for a similar problem?- Take the ADL questionnaire (see next section)- If in person (part of standard care, only collected by study staff, measurements performed by caregivers): Perform the following measurements: range of motion of the PIP joint of the affected finger (including noting any flexion contracture), distance fingertip to distal palmar crease (DPC), and grip strength using Jamar 2 setting.
Visit/Telephone call 4 (13-15 days after surgery)	
- Take the following questionnaire:
1. Are you able to return to activities of daily living, and what activities do you still have trouble doing? You can list the activities you are having trouble with.2. VAS3. How many oxycodone or other narcotic medications are you taking post-

	
op
 
4. Are you able to return to work?
 
5. Are you satisfied with the procedure, and would you choose to have it again for a similar problem?
 
- Take the ADL questionnaire (see next section)- If in person (part of standard care, only collected by study staff, measurements performed by caregivers): Perform the following measurements: range of motion of the PIP joint of the affected finger (including noting any flexion contracture), distance fingertip to distal palmar crease (DPC), and grip strength using Jamar 2 setting.-
Visit/Telephone call 5 (27-29 days after surgery)	
- Take the following questionnaire:
1. Are you able to return to activities of daily living, and what activities do you still have trouble doing? You can list the activities you are having trouble with.2. VAS3. How many oxycodone or other narcotic medications are you taking post-op4. Are you able to return to work?5. Are you satisfied with the procedure, and would you choose to have it again for a similar problem?- Take the ADL questionnaire (see next section)- If in person (part of standard care, only collected by study staff, measurements performed by caregivers): Perform the following measurements: range of motion of the PIP joint of the affected finger (including noting any flexion contracture), distance fingertip to distal palmar crease (DPC), and grip strength using Jamar 2 setting.-
Visit/Telephone call 6 (3 months +- 1 week after surgery)	
- Take the following questionnaire:
1. Are you able to return to activities of daily living, and what activities do you still have trouble doing? You can list the activities you are having trouble with.

	
2. VAS3. How many oxycodone or other narcotic medications are you taking post-op4. Are you able to return to work?5. Are you satisfied with the procedure, and would you choose to have it again for a similar problem? 
- Take the ADL questionnaire (see next section)- If in person (part of standard care, only collected by study staff, measurements performed by caregivers): Perform the following measurements: range of motion of the PIP joint of the affected finger (including noting any flexion contracture), distance fingertip to distal palmar crease (DPC), and grip strength using Jamar 2 setting.-
Visit/Telephone call 7 (6 months +- 1 week after surgery)	
- Take the following questionnaire:- 1. Are you able to return to activities of daily living, and what activities do you still have trouble doing? You can list the activities you are having trouble with.2. VAS3. How many oxycodone or other narcotic medications are you taking post-op4. Are you able to return to work?5. Are you satisfied with the procedure, and would you choose to have it again for a similar problem? 
- Take the ADL questionnaire (see next section)- If in person (part of standard care, only collected by study staff, measurements performed by caregivers): Perform the following measurements: range of motion of the PIP joint of the affected finger (including noting any flexion contracture), distance fingertip to distal palmar crease (DPC), and grip strength using Jamar 2 setting.

We will call or e-mail patients to ask them to complete questionnaires (see above) through Redcap.

Procedures

The intervention groups consist of:

- Open trigger finger release
 - o The A1 pulley is reached through a transverse incision under local anesthesia and monitored anesthesia care. It is then divided longitudinally. The patient is asked to flex and extend the affected finger. If triggering has been resolved, the wound is closed with sutures (12).
- Ultrasound-guided trigger finger release
 - o The A1 pulley is identified with the use of ultrasound. The pulley is released with a trigger finger device under local anesthesia and monitored anesthesia care (9).

Specific data variables to be collected

The variables that will be collected are:

- Range of motion of the PIP joint of the affected finger using a goniometer (in degrees), including any flexion contracture + Distance of fingertip from DPC
- Grip strength in the affected as well as contralateral hand using a dynamometer at Jamar 3 setting (in lbs)
- Return to activities of daily living. One question is: 'What activities can't you do?'. We also take a questionnaire to rate their ability to do certain activities (see questionnaire under this section). Patients can rate their ability to perform each activity on a scale from 1 to 5 (1 indicating no difficulty and 5 indicating unable to perform).
- VAS (a pain scale from 1 – 10, reported by the patient)
- How many oxycodone or other narcotic medications are you taking post-op? The number of pills taken will be given.
- Return to work. Patients give a date of when they started working again. Then we'll calculate the return to work in weeks
- Are you satisfied with the procedure, and would you choose to have it again for a similar problem? Answered with yes or no.
- Complications (i.e., trigger finger recurrence, infection, bleeding, etc.)

ADL questionnaire

Mass General Brigham Institutional Review Board
Intervention/Interaction Detailed Protocol

Opening jar	1	2	3	4	5
Driving	1	2	3	4	5
Household Chores	1	2	3	4	5
Carrying Groceries	1	2	3	4	5
Buttoning	1	2	3	4	5
Bathing	1	2	3	4	5
Cooking	1	2	3	4	5
Writing	1	2	3	4	5
Dressing	1	2	3	4	5
Shopping	1	2	3	4	5
Holding a book	1	2	3	4	5
Eating	1	2	3	4	5
Using a Computer	1	2	3	4	5
Holding a Phone	1	2	3	4	5
Using Toilet	1	2	3	4	5

Description of plans for return of research results as applicable

Not applicable

Definition of primary and secondary outcomes/endpoints

Primary endpoints:

- The 5 questions asked in the section above, together with the *ADL questionnaire*
- Recurrence of trigger finger or incomplete release

Secondary endpoints:

- Range of motion of the PIP joint of the affected finger (including noting any flexion contracture)
- Distance fingertip to distal palmar crease
- Grip strength in the affected hand
- Other complications than recurrence of trigger finger or incomplete release

Local site restrictions or site-specific procedures as applicable

The visits during the first 3 months are part of standard care. Patients with persistent problems will be seen at the 6-month follow-up as part of standard care. If they are doing well clinically, we will only contact them by phone or email to complete these questionnaires using Redcap (see above for the scheme).

Remuneration as applicable

There is no remuneration for this study.

2. Risks and Discomforts

Trigger finger release is a standard procedure (whether it is open or ultrasound-guided) for a trigger finger.

This study's foreseeable risks and discomforts include the time required to complete the measurements and questionnaires. All electronic information (like measurements in Excel files) will be stored on

password-protected computers in a locked office that only study staff members can access. Study data of the questionnaires will be collected and maintained electronically using REDCap, a secure and HIPAA-compliant web-based application to which only study staff will have access. This limits the risk of a data and confidentiality breach, though it is a possibility.

We do not foresee additional risks for subjects participating in the study. Subjects will receive usual care, regardless of their participation. Physicians will be readily accessible for consultation should a subject experience discomfort while completing the measurements and questionnaires or at any time during the study.

3. Benefits

Patients will not receive any direct benefits from this study. However, their participation will help us to determine clinical outcomes after ultrasound-guided and open trigger finger release, which can help patients and physicians in shared decision-making. Potential benefits of ultrasound-guided trigger finger release could be a faster recovery (faster return to work) and better patient-reported aesthetics.

4. Statistical Analysis

Normally distributed continuous data will be stated as mean \pm standard deviations, non-normally distributed continuous data as medians with interquartile ranges and categorical data as frequencies and percentages.

We plan to statistically compare the postoperative clinical data of open trigger finger release to ultrasound-guided trigger finger release.

We will use a student t-test to analyze normally distributed continuous data. When we compare data at two different time points within a group, we will use a paired student t-test. When we compare continuous data of two different groups, we will use an unpaired student t-test.

We will use a Mann-Whitney U test if the continuous data is not normally distributed.

We will use Fischer's exact test or a Chi-squared test for differences in categorical variables, depending on the number of events in the different groups.

Power analysis

We have performed a power analysis to find differences between two independent means (normally distributed) with alpha = 0.05, power = 0.80, and effect size 0.5. This would require a total sample size of 102 patients (51 in each group). If the data is non-normally distributed with the same alpha, power, and effect size, we would need a total of 106 patients (53 in each group).

This power analysis is performed for our most important primary outcomes: the 5-question and ADL questionnaires.

5. Monitoring and Quality Assurance

The full-time research coordinator and principal investigator are responsible for adherence to all IRB policies and guidelines and for the accuracy and completeness of all forms, entries, and informed consent.

Study data will be maintained in a locked filing cabinet and/or on password-protected computers. Questionnaires and self-reported responses will not become part of the subject's medical record. Hard copies of study-related data and forms will be stored in a lockable file cabinet. Only the investigators and study staff will have access to this information. Any magnetic or electronic information will be saved in password-protected computers, which only study staff members can access. REDCap, secure and HIPAA-compliant, will be used to collect all answers.

For guidance, refer to the following Partners policies:

Data and Safety Monitoring Plans and Quality Assurance

https://partnershealthcare-public.sharepoint.com/ClinicalResearch/DSMP_in_Human_Subjects_Research.pdf

Reporting Unanticipated Problems (including Adverse Events)

https://partnershealthcare-public.sharepoint.com/ClinicalResearch/Reporting_Unanticipated_Problems_including_Adverse_Events.pdf

6. Privacy and Confidentiality

- Study procedures will be conducted in a private setting
- Only data and/or specimens necessary for the conduct of the study will be collected

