Institutional Review Board Intervention/Interaction Detailed Protocol

Principal Investigator: [name]

Project Title: Clinical and Patient-Reported Outcomes After Ultrasound-guided vs. Open Trigger Finger Release

Version Date: 6/6/2023

For Intervention/Interaction studies, submit a Detailed Protocol that includes the following sections. If information in a particular section is not applicable, omit and include the other relevant information.

1. Background and Significance

Trigger finger is initially treated conservatively. Conservative treatment options include modification of activities, painkiller administration, splinting, and corticosteroid injections (1). Open or minimally invasive surgical treatment can be considered if conservative treatment fails. Minimally invasive surgery options consist of ultrasound-guided or blind percutaneous trigger finger release.

Many studies have reported good clinical outcomes after ultrasound-guided trigger finger release, including low rates of catching or locking recurrence rates, high QuickDASH scores and high patient satisfaction (2-4).

Postoperative clinical outcomes of open surgery have been widely compared to percutaneous surgery (5-8). However, the comparison of postoperative results between ultrasound-guided and open trigger finger release has been scarcely reported. Nikolaou et al. reported that ultrasound-guided trigger finger release resulted in a significantly sooner return to normal activities and better patient-reported cosmetic outcomes than open trigger finger release (9). Success rates and mean QuickDASH scores did not differ significantly between these groups in this cohort.

The potential benefits of ultrasound-guided trigger finger release compared to open trigger finger release have yet to be investigated. This study aims to prospectively analyze patient-reported outcomes in patients undergoing open vs. ultrasound-guided trigger finger release.

2. Specific Aims and Objectives

This study aims to prospectively analyze clinical and patient-reported outcomes in patients undergoing open vs. ultrasound-guided trigger finger release. Patients will not be randomly assigned to one of these two groups; rather, they will undergo the type of trigger finger surgery that they already agreed to with their surgeon, and we will measure the outcomes. Because of this, the study does not change the patient's standard of care; we are simply looking to collect additional data points.

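### Primary question 1 is worded with two different thresholds, has no rule for what counts as recovered, and leaves return to daily activities undated

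*Combined protocol and SAP*

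**What the plan says.** In section 6, Study Procedures, the Study visits table puts question 1 in the same words at every postoperative contact: "Are you able to return to activities of daily living, and what activities do you still have trouble doing". The contacts run from "Visit/Telephone call 2 (2-4 days after surgery") and "Visit/Telephone call 3 (6-8 days after surgery") through days 13-15 and 27-29 to 3 and 6 months.

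Later in section 6, under Specific data variables to be collected, the variable for return to daily activities is described differently: "One question is: 'What activities can't you do". The same entry introduces the 15-item ADL questionnaire, scored 1 to 5, with "1 indicating no difficulty and 5 indicating unable to perform".

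For work, the variable list says "Patients give a date of when they started working again", and the interval is then expressed in weeks. Daily activities have no equivalent.

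The first primary endpoint is "The 5 questions asked in the section above, together with the" ADL questionnaire. No time point, scoring rule or threshold is attached. The Statistical Analysis section offers t-tests, the Mann-Whitney test, and Fisher's exact or chi-squared tests. It names no time-to-event, interval-censored or repeated-measures method.

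**The concern.** Having trouble with an activity and being unable to do it are different states, and the protocol's own 1-to-5 scale separates them. If both describe one primary item, the free list can be collected or coded in two incompatible ways. The endpoint definition does not settle which governs, because the section it points back to could be the visit table or the variable list.

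The item is also compound. A patient may say yes, able to return, and still list ten activities. Nothing says whether that patient has recovered, so the decision could be left until the data have been seen. Being able to return is also not the same as having returned.

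Timing matters because the Background cites a previous comparison of these techniques that found "significantly sooner return to normal activities and better patient-reported cosmetic outcomes". Eligibility does not require employment, so a return-to-work date cannot cover everyone, whereas return to daily activities can.

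**Working it through.** **1. The two wordings on the protocol's own scale.** Read trouble as any score from 2 to 5, and cannot as a score of 5. A patient scoring 3 on all 15 items lists 15 activities under the first and 0 under the second. The same patient's ADL questionnaire shows fifteen 3s either way, so the ambiguity is confined to question 1.

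**2. What the schedule reveals about timing.** Taking nominal days 0, 3, 7, 14, 28, 91 and 182, the gaps are 3, 4, 7, 14, 63 and 91 days. A first yes brackets the return within one of these intervals. Resolution is fair in the first month and coarse after day 28.

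**3. Source of the arm size.** The Power analysis gives 51 per group (t-test) or 53 (non-normal data) for an effect size of 0.5, alpha 0.05 and power 0.80. A one-sided noncentral-t calculation gives n = 50.15, hence 51. Multiplying by π/3 for Mann-Whitney gives 52.52, hence 53. Two-sided, the figures would be 64 and 67; the plan does not state sidedness, which is a separate matter. I use 53 per arm and two-sided 0.05 below.

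**4. Yes/no at one contact.** Assume exponential recovery with median m days, so the proportion returned by day d is p(d) = 1 − 2^(−d/m). The medians are my assumptions. Power is the sum, over all pairs of counts (i, j), of Bin(i; 53, p1) × Bin(j; 53, p2) wherever the test gives p < 0.05. For medians of 7 and 14 days:

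| Day | p1 | p2 | Fisher | Chi-squared, uncorrected |
|---|---|---|---|---|
| 3 | 0.257 | 0.138 | 0.262 | 0.341 |
| 7 | 0.500 | 0.293 | 0.525 | 0.600 |
| 14 | 0.750 | 0.500 | 0.713 | 0.777 |
| 28 | 0.938 | 0.750 | 0.700 | 0.787 |

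Simulating the Fisher comparison gave 0.25 to 0.68, slightly lower. The enumeration has no simulation error, so I rely on it.

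**5. Using the timing.** A Mann-Whitney test was simulated on exact return days and on the visit intervals as ordered categories. Ranges cover repeated sets of runs. The Fisher and chi-squared columns apply the enumeration of step 4 to days 3, 7, 14 and 28.

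| Medians (days) | Fisher, worst to best contact | Chi-squared, best contact | Ranks on dates | Ranks on intervals |
|---|---|---|---|---|
| 7 v 14 | 0.26 to 0.71 | 0.79 | 0.84-0.86 | 0.82-0.85 |
| 7 v 11 | 0.13 to 0.36 | 0.44 | 0.48-0.51 | 0.47-0.50 |
| 10 v 14 | 0.07 to 0.21 | 0.28 | 0.31-0.32 | 0.29-0.30 |
| 4 v 7 | 0.08 to 0.52 | 0.62 | 0.69-0.70 | 0.67-0.68 |

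Dates add only about 1 to 2 points of power over intervals. The larger loss comes from testing one contact in isolation. It is smallest with the chi-squared test at the best contact, but that contact is day 14 in some scenarios and day 28 in others, and the plan nominates none.

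**The case against.** The strongest reply is that the question put to patients is identical at all six contacts and answers go into REDCap, so the variable-list sentence may be only a loose paraphrase. The ADL questionnaire, also primary, has one fixed scale and keeps difficulty and inability apart. No endpoint is defined as time to return to daily activities, and the Benefits section explains quicker recovery in parentheses as quicker return to work, which is dated. On this view the date field is a design preference.

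Much of that stands, and it rules out three stronger readings.

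- A reader might infer that speed of recovery cannot be measured. It can: six contacts give interval-censored return times, the graded questionnaire gives a trajectory from before surgery, and intervals lose little against dates.
- A reader might infer that the whole activity endpoint has no single meaning. That applies to question 1 only.
- A reader might infer that wording will vary by site, and therefore by arm. Nothing in the documents shows staff reading from the variable list.

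What the reply does not remove is that the variable list is where response formats are set (pill count, yes/no, date), so its wording cannot simply be ignored. Nor does it supply the missing rule for recovery, or a planned analysis that uses the visit intervals.

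**Conclusion.** The point holds as a definitional inconsistency in one primary item, together with inefficient use of its timing. The two thresholds and the absence of a recovery rule are plain on the page and need reconciling. The missing date is a cheap improvement and does not contradict anything in the plan.

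In the 7 v 14 day scenario, a single-contact Fisher test has power 0.26 to 0.71, against roughly 0.82 to 0.86 when timing is used. With an uncorrected chi-squared test at the best contact the shortfall against visit intervals is only a few points. These figures assume exponential recovery, contacts on nominal days, no loss to follow-up, and a yes that stays yes. They show the direction and rough size of the loss and do not predict the trial's power.

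**What to change.** Use the visit-table wording in both the table and the variable list, and split question 1 into three parts:

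- (a) whether the patient has returned to usual daily activities, yes or no;
- (b) if yes, the date, asked at each contact until the first yes;
- (c) which activities still cause any difficulty, stated to correspond to ADL scores of 2 to 5.

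State that (a) defines recovery for this item. Compare days from surgery to return between arms with a rank-based or time-to-event test that treats patients not yet returned as censored. If no date is added, analyse the visit intervals as ordered or interval-censored times; on the working above, this keeps nearly all the power.

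The cost is one reworded item and one date field in the visit table, variable list and REDCap form, plus a sentence in the Statistical Analysis section. No contact is added. The downside is that the date is recalled by the patient, as the return-to-work date already is.

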3. General Description of Study Design

Retrospective part

Patient characteristics and disease-related (trigger finger) variables will be collected retrospectively from patient charts on EPIC.

Prospective part

This will be a prospective two-arm study. Patients will either be treated with ultrasound-guided trigger finger release or open trigger finger release (conventional method). [name] is the only surgeon within the Mass General Brigham (MGB) hospitals that performs ultrasound-guided trigger finger release. All other surgeons perform open trigger finger releases.

Surgeons will measure range of motion and grip strength preoperatively and during postoperative visits, which is part of routine care. We will also administer questionnaires to see how patients are doing postoperatively. See the '6. Study Procedures' for a more elaborate description of the visits.

4. Subject Selection

Inclusion criteria:

1. ≥ 18 years of age
2. Clinical diagnosis of trigger finger
3. Patient has failed conservative treatment or elects not to undergo conservative treatment
4. Surgeon agrees that surgery is indicated
5. Subject agrees to complete follow-up questionnaires over a 6-month period

Exclusion criteria:

1. Prior surgery on the target finger
2. History of prior surgical pulley release in the target hand
3. History of prior surgical pulley release in the contralateral hand within 3 months of enrollment or with persistent symptoms that interfere with normal daily activities or work at the time of consent
4. Corticosteroid injection in the target finger or hand within 6 weeks of surgery
5. Presence of additional process in the target wrist or hand requiring additional intervention beyond pulley release (e.g., neurolysis, mass removal, tenosynovectomy)
6. Clinically significant trauma or deformity of the upper limb (shoulder to hand) on the target side
7. Clinically significant vascular disease (including Raynaud's phenomenon) of the upper limb (shoulder to hand) on the target side
8. Clinically significant neurological disorder (including complex regional pain syndrome) of the upper limb (shoulder to hand) on the target side
9. Planned surgical or interventional procedure on the contralateral wrist or hand

10. Systemic inflammatory disease (e.g., rheumatoid arthritis, lupus)
11. Amyloidosis
12. Diabetes not controlled by a stable dose of medication over the past three months
13. Pregnant or planning pregnancy in the next 6 months
14. Workers' compensation subjects

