15. Inability to provide a legally acceptable Informed Consent Form and/or comply with all follow-up requirements, including patients who do not speak English
16. Subject has other medical, social, or psychological conditions that, in the opinion of the investigator, preclude them from receiving the pre-treatment, required treatment, and post-treatment procedures and evaluations.
17. Trigger Thumb

How individuals are identified for recruitment, including description of the use of recruitment materials such as flyers, brochures, advertisements, letters, etc.

We are selecting patients interested in undergoing surgical treatment for a trigger finger. Thus, these patients are being seen by a hand surgeon at one of the hospitals within the MGB system (MGH main campus, MGH MGH Waltham, MGH Danvers, BWH main campus, BWH Faulkner and BWH Foxborough) for a trigger finger.

Who is responsible (role on research team) for identifying and recruiting individuals

The orthopedic surgeons and study staff at one of the MGB hospitals (MGH main campus, MGH MGH Waltham, MGH Danvers, BWH main campus, BWH Faulkner, and BWH Foxborough).

When individuals are recruited

Individuals are recruited when indicated for trigger finger release at the outpatient clinic if eligible.

Where individuals are recruited

Patients are recruited at the outpatient clinic of one of the MGB hospitals (MGH main campus, MGH MGH Waltham, MGH Danvers, BWH main campus, BWH Faulkner, and BWH Foxborough).

How recruitment goals match the prevalence rates of the condition/disease being studied and the populations most impacted by the condition/disease being studied

Trigger finger release is a very common procedure to relieve symptoms of a trigger finger. Many patients get treatment for this disease within the MGB hospitals (MGH main campus, MGH MGH Waltham, MGH Danvers, BWH main campus, BWH Faulkner, and BWH Foxborough). The prevalence is higher in diabetic patients than in the general population (10, 11). The recruitment goals will match the prevalence rates of the condition as it is a very common disease, and many patients with comorbidities (i.e., diabetes, thyroid disease) receive treatment within the MGB hospitals (MGH main campus, MGH MGH Waltham, MGH Danvers, BWH main campus, BWH Faulkner and BWH Foxborough).

Methods to enhance enrollment of diverse individuals and under-represented populations

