We will include all patients who meet the inclusion criteria. We do not exclude patients based on race, color, national origin, sex, sexual orientation, or religion. We will not enroll vulnerable patient populations in this study.

5. Subject Enrollment

Patients will be prescreened through retrospective manual chart review.

Patients will be contacted in person at one of the MGB hospitals (MGH main campus, MGH Waltham, MGH Danvers, BWH main campus, BWH Faulkner, and BWH Foxborough). Patients who meet the inclusion criteria will get a summary of the study by an orthopedic surgeon or a study staff member to see if they are interested. If patients are interested, they will receive the study fact sheet, and the surgeon or study staff member will explain the study in more detail and answer any questions the patient may have. Subjects will be asked to complete the questionnaire either in person or over email or telephone before surgery. Subjects who opt to not complete the questionnaire in person will be contacted using the email or telephone script approved in this study. Subjects who do not complete the pre-op questionnaire before surgery will be withdrawn. Subjects can opt to receive an encrypted or unencrypted email. Subjects who indicate verbally in the outpatient clinic that they do not wish to participate will not be included in the study.

Depending on the treating surgeon, patients will either be treated with an open trigger finger release or an ultrasound-guided trigger finger release.

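### Narcotic use is a primary question at all six postoperative contacts but has no preoperative value, so use that predates surgery may be counted in the comparison of arms

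*Combined protocol and SAP*

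**What the plan says.** All in the combined protocol and SAP.

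- **Section 6, Study visits.** Before surgery the patient-reported items are the ADL form and pain: "ADL questionnaire (see next section)- Visual analog scale for pain (VAS): pain on a scale of 1 to 10". Hand measurements are also taken. No narcotic question is listed. At contacts 2 to 7 (days 2-4, 6-8, 13-15 and 27-29, then 3 and 6 months) the third question is "How many oxycodone or other narcotic medications are you taking post-op".
- **Section 6, Specific data variables.** The answer is recorded as a count: "The number of pills taken will be given". No indication is recorded and nothing is subtracted for earlier use.
- **Section 6, Definition of primary and secondary outcomes.** The first primary endpoint is "The 5 questions asked in the section above, together with the" ADL form, so narcotic use is one of five primary questions. The power analysis names this set among its most important outcomes.
- **Section 4, Subject Selection.** None of the 17 exclusions names narcotic use or chronic pain. Criterion 16 is a discretionary catch-all.
- **Sections 2, 3 and 5.** Patients are not randomised; the arm depends on the treating surgeon. One surgeon does every ultrasound-guided release, and "All other surgeons perform open trigger finger releases".
- **Section 5, Subject Enrollment.** The preoperative form is compulsory: "Subjects who do not complete the pre-op questionnaire before surgery will be withdrawn".
- **Statistical Analysis.** Postoperative data are compared between arms by t-test, Mann-Whitney, Fisher or chi-squared test. Paired t-tests are planned for two time points within a group. No adjustment is named.

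**The concern.** A patient who takes narcotics for another condition can report the same pills at every postoperative contact. The item does not tell the patient to leave out medication that was already in use. Pain and ADL at least have a Visit 1 value that could be used to judge change. Narcotic use has none, so a within-group comparison with the preoperative state cannot be made, and the between-arm comparison cannot be adjusted from the study forms.

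Under randomisation, prior users would be balanced on average. Here the arm follows the surgeon, so any difference in case mix between one surgeon's patients and everyone else's passes directly into the count. What is at stake is a difference in existing users being reported as a difference between techniques. It matters most at the 3- and 6-month contacts, where a reader will want to know whether anyone has started and continued narcotics since the operation.

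**Working it through.** **Step 1. Is there a preoperative value?** Setting Visit 1 beside contacts 2 to 7 in Section 6: ADL and VAS appear at all seven, the narcotic item at six, and the missing one is Visit 1. The list of variables and the chart-review description in Section 3 do not name it either.

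**Step 2. The sample size used below.** The plan states 51 per group for effect size 0.5, alpha 0.05 and power 0.80. The normal approximation, one-sided, is n = 2(1.645 + 0.842)² / 0.5² = 49.5, so 50. The noncentral t gives 50.15, so 51, as stated. Dividing 50.15 by 0.955 for Mann-Whitney gives 52.5, so 53, also as stated. A two-sided test would need 64. The unstated sidedness is a separate matter, and nothing here depends on it beyond taking n = 51.

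**Step 3. Illustration on any use at a late contact.** Assumptions, none from the documents: the operation causes no use at that contact, all reported use predates surgery, and the prior-use rates in the two arms are p1 and p2. The chance of a significant result is the sum, over all x and y from 0 to 51, of Bin(x; 51, p1) × Bin(y; 51, p2), counting only pairs whose two-sided p is below 0.05. The plan allows Fisher or chi-squared (here uncorrected) for categorical data.

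| Assumed prior use | Fisher | Chi-squared |
|---|---|---|
| 5% vs 5% | 0.8% | 4.4% |
| 2% vs 5% | 1.6% | 9.6% |
| 5% vs 8% | 2.9% | 8.4% |
| 5% vs 10% | 6.6% | 14.7% |
| 5% vs 15% | 25.2% | 39.3% |
| 5% vs 20% | 52.1% | 65.6% |

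The expected numbers of users at 5% vs 15% are 0.05 × 51 = 2.6 and 0.15 × 51 = 7.7. A realised split of 3 vs 8 gives Fisher p = 0.20, so a typical trial at those rates would not be significant. The 25% comes from the trials with a wider split.

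**Step 4. The same question on the pill count.** The plan records a count, for which it would use a t-test or Mann-Whitney. With non-users at zero and prior users at positive counts, a simulated Mann-Whitney test rejects about 15% of the time at 5% vs 10% and about 39% at 5% vs 15%, close to the chi-squared column. On the mean scale, the false difference is (difference in prevalence) × (extra pills per prior user, in SD). For a 5-point imbalance and 2 SD it is 0.05 × 2 = 0.1 SD. For a 10-point imbalance and 4 SD it is 0.10 × 4 = 0.4 SD, against a planned effect of 0.5 SD. The 2 to 4 SD range is also assumed.

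**The case against.** **The wording may already limit the answer.** In a questionnaire about recovery, some patients will take post-op to mean pills for the operation. That stands. A reader might infer that prior use is certainly counted at all six contacts, but the documents do not support this: the word can be read as a reason or as a time, and no instruction settles it. *May be counted* is as far as the text goes.

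**The chart may hold the value.** Patients are prescreened by chart review, and unitemised patient characteristics are taken from EPIC. Silence about narcotics does not show that prior use is unavailable, since the protocol does not itemise any of those characteristics. So it would be too strong to say that new persistent use can never be identified. What stands is that the planned data do not separate it: the variable is not named and no analysis uses it.

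**Criterion 16 could screen some users out.** It covers a case where "Subject has other medical, social, or psychological conditions that, in the opinion of the investigator, preclude them" from the procedures and evaluations. A stable user can usually complete all of these, and the criterion does not name narcotics.

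**The illustration uses chosen rates and a test on any use that the plan does not define.** Both parts are fair. Nothing in the documents suggests a threefold imbalance between surgeons in one hospital system, and with Fisher the milder cases stay below 5%. Two things limit the objection. Fisher's own rate under equal 5% prevalence is only 0.8%, so 2.9% is still a rise. And the Mann-Whitney test that the plan would use on a skewed count rejects more often, not less.

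**ADL and VAS are not protected either.** This is true: they have a Visit 1 value, but the between-arm analysis names no adjustment for it. The root is surgeon-based allocation with unadjusted tests. The narcotic item differs in that the value needed for adjustment is not collected.

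**Conclusion.** The point holds as a gap in data collection for one of the five primary questions. It is certain that no preoperative narcotic value is specified, that existing users are not excluded by name, that arms follow the surgeon, and that postoperative values are compared without adjustment. It follows that earlier use may enter the count and may differ between arms, and that new and continuing use are not separated at 3 and 6 months.

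The size cannot be derived from the documents. The rejection rates range from near nothing to large because they rest entirely on assumed prevalences and on assuming no late use caused by surgery. A reader might take the 25% figure as this trial's false-positive rate; it is not, and the documents give no reason to prefer 5% vs 15% over 5% vs 8%. Likewise, the idea that late use mostly reflects prior users is a clinical assumption with no figure behind it. The case for acting is that, without the baseline, nobody can check the imbalance from the study forms, and collecting it costs very little. This is a worthwhile cheap improvement and does not threaten the study as a whole.

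**What to change.** 1. Add a question on current narcotic use to the Visit 1 questionnaire, in the same units as the postoperative item.
2. For patients already enrolled, take the value from the chart where possible, and flag its source.
3. Report the between-arm comparison of narcotic use adjusted for preoperative use.
4. Show new use separately, by arm, among patients not taking narcotics before surgery.

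Cost: one more question on a form that every subject must already complete, and a minor amendment; no extra visit or staff. Some patients already enrolled will still lack a baseline value, and chart records may not match self-report, so the number missing and the source should be reported.
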